## **Criteria:**

All colonoscopies in the study will be performed by a qualified professional. Patients will be 40 and older and will be randomized to receive colonoscopy with or without the Endocuff. Data collected will include the type of scope used (adult versus pediatric), age, gender, indication, history of prior abdominal surgery and type, identification of diverticulosis classified as mild moderate or severe, insertion time, total procedural time, total withdrawal time, inspection time (withdrawal time minus anytime suctioning, cleaning, and diagnostic biopsy or therapeutic procedure), and polypectomy time for each polyp removed. For each polyp, we will record the location, size, shape, and pathology.

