### **Inclusion criteria**

- Referral for screening or surveillance colonoscopy
- Ability to provide informed consent
- 40 years and older

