### Statistical Analysis and Sample Size:

- Normally distributed continuous variables will be summarized using means and standard deviations while non-normally distributed continuous variables will be summarized using medians and ranges.
- The primary endpoints for the study will be the inspection time and insertion time, , the total time per polypectomy, and the total procedure time.
- The secondary endpoints will be total time per polypectomy, total procedure times, and adenomas detected.
- All colonoscopies in the study will be performed by a qualified professional. Patients will be 40 and older and will be randomized to receive colonoscopy with or without the Endocuff. Data collected will include the type of scope used (adult versus pediatric), age, gender, indication, history of prior abdominal surgery and type, identification of diverticulosis (classified as mild moderate or severe), insertion time, total procedural time, total withdrawal time, inspection time (withdrawal time minus anytime suctioning, cleaning, and diagnostic biopsy or therapeutic procedure), and polypectomy time for each polyp removed. For each polyp, we will record the location, size, shape, and pathology.

There will be a sample size of 200 subjects enrolled in this study. 100 randomized into two groups. With the sample size of 100 per group, the study will have 80% power to detect a 1 minute difference in the inspection time between the two groups. The inspection and insertion times will be compared using a two-sided two sample t-test, 5% significance level, and standard deviation of 2.5 minutes.

The data will be analyzed and the statistics performed by persons in the biostatistics department.

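### The t-test of inspection and insertion times is sound; prespecified adjustment for four variables already collected is a cheap improvement with a possible, not assured, gain in power

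*Combined protocol and SAP*

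**What the plan says.** All places cited are in the combined protocol and SAP.

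- **Analysis.** Under Statistical Analysis and Sample Size: "The inspection and insertion times will be compared using a two-sided two sample t-test, 5% significance level". The same sentence gives an SD of 2.5 minutes. No regression model, covariate adjustment or stratified randomisation is described anywhere.
- **Power.** The same section states: "With the sample size of 100 per group, the study will have 80% power to detect a 1 minute difference in the inspection time". No target difference is given for insertion time or any other time.
- **Variables collected.** Under Criteria, and again in the statistical section: "Data collected will include the type of scope used (adult versus pediatric), age, gender, indication, history of prior abdominal surgery and type". The list continues with "identification of diverticulosis classified as mild moderate or severe".
- **Population.** The first inclusion criterion is "Referral for screening or surveillance colonoscopy", so indication has two levels.
- **Per-polyp data.** The trial also records "polypectomy time for each polyp removed".

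**The concern.** Randomisation makes the unadjusted comparison valid. A baseline variable that predicts the outcome can still remove some residual variance and narrow the confidence interval. The trial records four such candidates and gives them no role in the comparison of the times.

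The design has little slack: on the exact t-test, 100 per arm is the smallest size that reaches 80% (99 per arm gives 79.97%). What is at stake is a modest amount of precision that might be had without enrolling anyone else. The validity of the result is not in question.

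**Working it through.** **Inputs from the statistical section:** difference 1 min (inspection time only), SD 2.5 min, n = 100 per arm (N = 200), two-sided 5%.

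**Assumed input:** R-squared, the share of variance in inspection time explained by the covariates. The documents give no value, so it is varied from 0 to 0.10.

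**Covariates:** age (linear), gender, indication (screening or surveillance) and prior abdominal surgery (yes/no), so p = 4 degrees of freedom.

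**Step 1. Reproduce the plan's figure.**
- SE = 2.5 × √(2/100) = 0.3536 min.
- Noncentrality = 1/0.3536 = 2.828, with df = 198 and critical t = 1.972.
- Noncentral t power = 80.4%, which agrees with the stated 80%.
- 95% CI half-width = 1.972 × 0.3536 = 0.697 min.

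**Step 2. Add four covariates.**
- df = N − 2 − p = 194, critical t = 1.972.
- Variance = 2.5² × (1 − R²) × (2/n) × [1 + p/(N − p − 3)].
- The last factor is 1 + 4/193 = 1.0207. It is the average price of chance imbalance in the covariates.

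| Assumed R² | SE (min) | Noncentrality | Power | CI half-width (min) | Equivalent unadjusted n per arm |
|---|---|---|---|---|---|
| 0 | 0.3572 | 2.800 | 79.6% | 0.704 | about 98 |
| 0.02 | 0.3536 | 2.828 | 80.3% | 0.697 | about 100 |
| 0.05 | 0.3482 | 2.872 | 81.5% | 0.687 | about 103 |
| 0.10 | 0.3389 | 2.951 | 83.6% | 0.668 | about 109 |

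**Step 3. Break-even.** Adjusted power equals unadjusted power at R² of about 0.021. Most of this comes from the imbalance factor: 1 − 1/1.0207 = 0.020. The remainder is the four lost degrees of freedom. Adjusted power falls below 80.0% when R² is under about 0.011.

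**Step 4. Check by simulation** (100,000 trials per cell, one continuous and three binary covariates). Power was 79.8%, 80.4%, 81.5% and 83.5% at R² of 0, 0.02, 0.05 and 0.10, within 0.3 points of the formula. At R² = 0.05 the type I error of the adjusted test was 4.93% and 5.02% in two runs with normal errors. With skewed errors (assumed lognormal, log-SD 0.6) it was 4.93% and 4.97%. Power with those skewed errors (20,000 trials) was 79.6%, 81.5% and 83.4% at R² of 0, 0.05 and 0.10, so this degree of skew does not change the comparison.

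**The case against.** The strongest case against raising this is that nothing is wrong. The test, sidedness, significance level, SD and sample size are stated and agree with one another, so preferring a linear model to a valid prespecified t-test is a matter of choice. The benefit rests on an R-squared that the documents do not supply, and values from 0.01 to 0.10 have no more textual support than larger ones. Over that range the interval barely moves: each side narrows by 0.010 min (0.6 seconds) at R-squared 0.05 and by 0.029 min (1.7 seconds) at 0.10. Every figure concerns inspection time, because no target difference is given for insertion time. Finally, the documents differ on which times are primary, and settling that matters more.

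All of this stands and sets the priority. It does not remove the point, because the possible gain costs almost nothing and the worst case is small and known.

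Some stronger readings are tempting, and the documents do not support them:

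- **The t-test is biased or underpowered.** It is neither, on the plan's own inputs.
- **Adjustment would give a large gain.** That needs a high R-squared, for which the documents offer no evidence.
- **The plan leaves covariates open to choice after the data are seen.** The stated comparison has no covariates to choose.
- **Operator should be in the model.** The documents say only "All colonoscopies in the study will be performed by a qualified professional". They do not give the number of operators or list operator among the data collected.
- **Every recorded patient characteristic should be used.** Diverticulosis is identified during the procedure, after allocation, and could be affected by the device. The documents do not say whether scope type is chosen before the allocation is known.

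**Conclusion.** The point holds as an optional improvement. The planned unadjusted t-test is valid and adequately powered (80.4%). Adjusting for four variables already collected changes power for inspection time by −0.8, −0.0, +1.2 or +3.2 percentage points at assumed R-squared 0, 0.02, 0.05 or 0.10, so a gain is possible but not assured.

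The conclusion rests on three assumptions:

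- R-squared exceeds about 0.021, if there is to be any gain.
- The covariates take four degrees of freedom. Finer coding of indication or type of surgery would cost slightly more.
- All four variables are known before the procedure. This is inferred from their nature, since the documents do not say when they are recorded.

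For insertion time the same reasoning applies, but its size cannot be given.

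**What to change.** In Statistical Analysis and Sample Size:

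1. Make the main analysis of inspection time and of insertion time a prespecified linear model of time on arm plus age (continuous), gender, indication (screening or surveillance) and prior abdominal surgery (yes/no).
2. Report the adjusted mean difference with its 95% CI, and keep the two-sample t-test as a sensitivity analysis.
3. State how a missing covariate value is handled, so that no randomised subject is dropped because of it.
4. State that diverticulosis and scope type are not adjusted for.
5. Do not apply this model to per-polyp polypectomy times, which exist only for subjects with polyps and can repeat within a subject.

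**Cost:** SAP wording, the coding and missing-value decisions above, and one extra analysis as sensitivity. No new data or subjects are needed. The statistical cost is at most about 0.8 percentage points of power, if the covariates explain nothing.

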## Introduction:

Endocuff Vision ( Olympus) is a disposable device that has 8 independently moving soft flexible arms arranged in a single row. The device comes in several sizes and can fit the tips of most commonly used colonoscopes. During intubation, the arms fall flat to the body of the scope as not to impede forward motion. Endocuff Vision is an FDA approved device that fits over the end of a colonoscope and has flexible soft fingers that project from the sides. These fingers can be used to pull back the folds in the colon and expose mucosa on the proximal sides. A number of studies indicate that Endocuff improves the adenoma detection rate (ADR) during colonoscopy. In a non-randomized retrospective evaluation, Endocuff resulted in better detection, faster insertion, and faster inspection (1).

Our aim in this study is to show in a prospective randomized trial Endocuff Vision could improve insertion because during loop withdrawal the cuff tends to stabilize the position of the tip, preventing its backward movement and speeding loop removal. Similarly, during inspection, the main goal is to evaluate the proximal sides of folds and flexures. The process is made easier and quicker by the device. Third, during polypectomy, Endocuff Vision helps to stabilize the position and the scope tip.

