## **Objectives:**

*Primary objectives* of the study are:

- To compare the insertion time, inspection time, the total time per polypectomy, and the total procedure time during High Definition colonoscopy with Endocuff Vision versus standard High Definition colonoscopy.

*Secondary objectives:*

- To compare the number of adenomas detected per subject with High Definition Endocuff Vision compared to Standard High Definition colonoscopy.
- To compare the detection rates for polyp subtypes (including advanced adenomas, serrated polyps, right sided adenomas, etc) for High Definition Endocuff Vision compared to Standard High Definition colonoscopy.

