## **Primary End-point:**

- The inspection time will be shorter because the proximal sides of the folds are more quickly exposed with Endocuff Vision compared to standard colonoscope alone because of the ability of the Endocuff Vision to stabilize the position of the colonoscope tip during loop withdrawal, thus preventing its backward movement and speeding loop removal.

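### Does the lack of a named test or interval for adenomas detected call for a change to the analysis section?

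*Combined protocol and SAP*

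**What the plan says.** The combined protocol and SAP deals with adenoma detection in four places.

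- **Objectives.** The first secondary objective is "To compare the number of adenomas detected per subject with High Definition Endocuff Vision compared to Standard High Definition colonoscopy". The second is "To compare the detection rates for polyp subtypes (including advanced adenomas, serrated polyps, right sided adenomas, etc", which concerns a separate set of outcomes.
- **Statistical Analysis and Sample Size.** The endpoint list reads "The secondary endpoints will be total time per polypectomy, total procedure times, and adenomas detected". The only comparison specified is "The inspection and insertion times will be compared using a two-sided two sample t-test, 5% significance level, and standard deviation of 2.5 minutes". The only other analysis rule is descriptive: normally distributed continuous variables get means and standard deviations, and "non-normally distributed continuous variables will be summarized using medians and ranges".
- **Criteria.** The raw data for the count will exist: "For each polyp, we will record the location, size, shape, and pathology".
- **Introduction.** Prior evidence is cited in terms of another measure: "A number of studies indicate that Endocuff improves the adenoma detection rate (ADR) during colonoscopy".

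The trial is sized on inspection time alone: 100 per group, 80% power, a 1-minute difference and a standard deviation of 2.5 minutes. No adenoma mean, variance or detection rate is given anywhere.

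**The concern.** The Primary End-point section predicts that "The inspection time will be shorter because the proximal sides of the folds are more quickly exposed with Endocuff Vision". Inspection exists to find lesions, so a shorter inspection is welcome only if detection does not suffer. The documents do not draw that link. It is a reviewer's judgement, though a natural one, and it makes the adenoma result more than a footnote.

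The analysis section nevertheless gives that result no test, effect scale or interval. Adenoma counts are skewed and mostly 0 or 1. A mean difference, a rank test, the proportion of subjects with at least one adenoma and a Poisson ratio can point different ways on the same data. Someone could choose among them after seeing the results. The medians-and-ranges rule, if applied to the count, could show two equal medians when detection differs. A bare non-significant p-value from 100 per arm could also be misread as evidence that detection was preserved.

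**Working it through.** **1. The plan's own figure.** Inputs from Statistical Analysis and Sample Size: difference 1 minute, SD 2.5 minutes, 100 per group, two-sided 5%.

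- Standard error = 2.5 × √(2/100) = 0.354, and 1/0.354 = 2.83.
- Power = Φ(2.83 − 1.96) = 80.7% by the normal approximation, or 80.4% by the noncentral t.
- The required size is 99 per group by the normal approximation and 100 by the t-test.

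The stated figure reproduces. It concerns inspection time only, so there is no adenoma figure to check.

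**2. Which parts are missing.**

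| Element | Where it stands |
|---|---|
| Measure | Stated in Objectives: number per subject |
| Data | Stated in Criteria: pathology for each polyp |
| Test | Not stated |
| Effect measure and interval | Not stated |

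The other wordings do not compete with the stated measure. Subtype detection rates are a different objective, and the adenoma detection rate in the Introduction describes other studies. Adenomas detected, in the endpoint list, reads as shorthand for the count in Objectives.

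**3. Assumptions for the rest.** Negative binomial counts, control mean μ = 0.8 or 1.0, variance/mean φ = 2, n = 100 per arm. These are assumptions, because the documents supply none. The chance of a zero count is φ^(−μ/(φ−1)), which is 2^(−0.8) = 0.574 or 2^(−1) = 0.500.

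**4. Does the only named test fail on such counts?** With equal detection, the simulated rejection rate of the two-sample t-test was 0.048 to 0.054 across separate runs. It holds its 5% level.

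**5. How much turns on the choice of test?** Suppose the true ratio is 0.75.

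- With three candidates (t-test, Wilcoxon, chi-square on any adenoma), at least one is significant in 0.328 (μ = 0.8) or 0.385 (μ = 1.0) of trials, and all three in 0.150 or 0.175. The differences are 0.178 and 0.210.
- The chi-square test answers a question about a proportion, while the stated measure is a count. Without it, the t-test and Wilcoxon disagree in about 12 to 14% of trials.
- With equal detection, at least one of those two tests is significant in about 7.4% of trials.

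**6. The Poisson figure.** A Poisson test that ignores overdispersion has type I error 2 × (1 − Φ(1.96/√2)) = 0.166 at φ = 2. The arithmetic is right, but the plan names no Poisson model.

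**7. The power figure.** At ratio 0.75, SE = √(φ/n × (1/μ + 1/(0.75μ))).

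- μ = 0.8: √(0.02 × 2.917) = 0.2415; power = Φ(0.2877/0.2415 − 1.96) = 0.221.
- μ = 1.0: √(0.02 × 2.333) = 0.2160; power = Φ(0.2877/0.2160 − 1.96) = 0.265.

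A prespecified negative binomial model gives about 24 to 29%, which is essentially the same. The low power comes from 100 per arm, not from the missing sentence.

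**8. The medians.** At ratio 0.75 the two arm medians coincide in about 92% (μ = 0.8) or 46% (μ = 1.0) of trials, and in 23 to 100% over wider assumptions (μ 0.5 to 1.0, φ 1.5 to 3). A median would be a poor summary of this count. The rule, however, is written for continuous variables and for summaries. It does not govern how the arms are compared.

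**The case for a change.** The best case for a change is that a secondary endpoint still deserves a stated analysis. The sentence that assigns the statistics to the biostatistics department says who will do the work, not what they will do. A choice left unrecorded until the data are in is the kind of freedom an analysis plan is meant to remove. The cost would be a few lines of text, with no new data and no change in sample size. Because detection is under-powered, an interval is the useful result, and the plan promises none.

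Part of this stands. The test, effect measure and interval are absent, and some freedom remains: about 12 to 14% of trials under the assumed drop in detection. A prudent analyst would report an interval.

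The rest is weaker. The measure is not open, so the proportion-based comparison, and the 18 to 21% that depends on it, falls away. The Poisson error rate describes a misuse that nothing in the plan invites. Low power would be the same under any wording. A negative binomial model would be a reasonable choice, but it would replace no worse stated method; a difference in means with the t-test already in the plan would serve as well. Adenomas are also not special here: total time per polypectomy and total procedure time have no named test either, so the point reflects how brief the section is.

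**Conclusion.** No change is called for. The gap is real but is one of detail. No stated rule produces a wrong adenoma result, and no stated number is in error. The stated objective points to a comparison of adenomas per subject, the pathology data to build the count are collected, and the one test the plan names behaves properly on counts of this kind at 100 per arm. Biostatisticians given this objective would compare the counts and show an interval without being told to.

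What remains is a modest choice between a mean-based and a rank-based comparison of one secondary outcome. It changes significance in about one trial in eight if detection truly falls by a quarter. That size rests on an assumed control mean of 0.8 to 1.0 and a variance twice the mean, neither of which the documents supply. At that mean and variance, the 95% limits around an observed ratio of 1 would run from about 0.65 to 1.55 (mean 0.8) or 0.68 to 1.48 (mean 1.0). The trial can therefore say little about detection however the analysis is worded, and the reading of the primary time comparison is unaffected.

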### Safety Risks to the patient and Data integrity:

All paper charts pertaining to the patient will be kept under lock and key in coordinators office away from the endoscopy area. The data entry will be performed into an excel file which will be stored on an internal network drive with encryption and password security. Data management will include double data entry and regular back-up of the data. Only approved personnel by the IRB will have access to the file storage. This file will also not have any identifiable information. A study log with the identifiable information will be kept in a separate folder to enable the investigators to assist in any research audit. No procedural data except the date of examination will be entered into this log.

Any subject who wishes to withdraw from this investigation on his/her own accord and for whatever reason is entitled to do so without obligation and prejudice to further treatment. In addition, the Investigator may decide for reasons of medical prudence, to withdraw a subject. In either event, the Investigator will clearly document the date and reason(s) for the subject's withdrawal from this investigation in the CRF and should indicate whether or not he considers it was related to the study interventions.

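### Does the plan need a written end point and a rule for unfinished insertions before insertion time can be compared by t-test?

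*Combined protocol and SAP*

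**What the plan says.** Insertion time is in the primary objective (Objectives: "To compare the insertion time, inspection time, the total time per polypectomy, and the total procedure time") and on the list of primary endpoints (Statistical Analysis and Sample Size: "The primary endpoints for the study will be the inspection time and insertion time"). The Primary End-point section, however, states its hypothesis for inspection time alone: "The inspection time will be shorter because the proximal sides of the folds are more quickly exposed with Endocuff Vision". The power statement is also written for inspection time only.

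The planned comparison is: "The inspection and insertion times will be compared using a two-sided two sample t-test, 5% significance level". The same sentence gives a "standard deviation of 2.5 minutes".

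The data items under Criteria are repeated under Statistical Analysis and Sample Size. They include "insertion time, total procedural time, total withdrawal time, inspection time (withdrawal time minus anytime suctioning". Inspection time is explained in brackets; insertion time appears by name only. The list is introduced as what the data will include, so it is not a closed list, and the case report form itself is not among the documents.

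The nearest rule on incomplete participation is in Safety Risks to the patient and Data integrity, for subjects who withdraw or are withdrawn: "In either event, the Investigator will clearly document the date and reason(s". It does not cover a subject who stays in the study with an incomplete insertion. No analysis set is named.

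**The concern.** A t-test needs one number per patient, and an unfinished insertion has no completed time. The analyst has to leave the patient out, enter the time at which the attempt stopped, or impute. With no rule written down, that choice could be made after the data are seen.

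Failed insertions are likely to be among the harder ones, so dropping them trims the slow tail. If more are trimmed from the cuff arm, the cuff looks faster than it is. If more are trimmed from control, a real benefit is partly hidden. The second case is plausible on the protocol's own reasoning, since the Introduction argues that "Endocuff Vision could improve insertion because during loop withdrawal the cuff tends to stabilize the position of the tip". Equal completion between arms therefore cannot simply be assumed, and the comparison at stake is listed as primary.

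**Working it through.** **Inputs.** From Statistical Analysis and Sample Size: 100 per group, two-sided 5%, SD 2.5 minutes, 1-minute target. Not in the documents, hence assumed: the number of failures per arm, the link between failure and difficulty, and (for the simulations) lognormal times with mean 6 minutes. The plan states its SD in the sentence covering both times; using it for insertion time follows that sentence.

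**The plan's own figure.** The standardised difference is 1 / (2.5 × √(2/100)) = 2.83. Power = Φ(2.83 − 1.96) = 80.7%; the noncentral t with 198 degrees of freedom gives 80.4%. The sample size is 2 × [(1.960 + 0.842) × 2.5]² = 98.1, so 99 per group. The stated 80% with 100 per group reproduces.

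**Bias if failures are dropped, closed form.** Suppose there is no true effect and times are normal. A fraction f of an arm is lost, namely those highest on a difficulty score that correlates ρ with insertion time. The completers' mean then moves by −ρ × SD × h(f), where h(f) = φ(q)/(1 − f) and q is the (1 − f) normal quantile. The values are h(2%) = 0.0494, h(3%) = 0.0701 and h(5%) = 0.1086.

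With ρ = 0.5, ρ × SD = 1.25. Differences are cuff minus control, so a negative value favours the cuff:

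- 3 vs 2 lost: −1.25 × (0.0701 − 0.0494) = −0.03 min
- 3 vs 0 lost: −1.25 × 0.0701 = −0.09 min
- 5 vs 0 lost: −1.25 × 0.1086 = −0.14 min

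**Simulation with lognormal times** (mean 6, SD 2.5, no true effect, pooled t-test). The nominal cuff-favouring error is 2.5%. Repeat runs of the ρ = 0.5 rows differ by a few tenths of a percentage point.

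| Lost, cuff vs control | Shift, ρ = 0.5 | Cuff-favouring error, ρ = 0.5 | Shift, slowest patients lost | Cuff-favouring error, slowest patients lost |
|---|---|---|---|---|
| 3 vs 2 | −0.03 min | 3.2% | −0.07 min | 5.3% |
| 3 vs 0 | −0.09 min | 4.4% | −0.24 min | 10.8% |
| 5 vs 0 | −0.15 min | 6.1% | −0.35 min | 19.3% |

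Reversing the imbalance reverses the sign: with the slowest 0 vs 3 lost, the shift is +0.23 min and the control-favouring error is 10.7%. With 3 vs 3 lost the shift is 0.

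**Bias if the stopping time is entered instead.** The shift is (cuff failure rate − control failure rate) × (stopping time − mean time). With 2% failing in the cuff arm and 5% in control:

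- attempts stopped 10 minutes later than the mean: (0.02 − 0.05) × 10 = −0.30 min
- attempts stopped 3 minutes earlier than the mean: (0.02 − 0.05) × (−3) = +0.09 min

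Bias of either sign is therefore possible.

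**Loss of power if failures are equal and dropped.** Power for 1 minute is 80.0% at 2% lost (98 per group), 78.7% at 5% (95) and 76.5% at 10% (90).

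**The obvious replacement.** Rank every failure worst and use the rank-sum test. When the failures really are the slowest patients, cuff-favouring error stays at 2.2% to 2.5%, but that check is nearly circular: ranking them last almost restores the true order. With ρ = 0.5 and 5 vs 0 failures, the worst-rank test gives 1.2% cuff-favouring and 4.1% control-favouring error. Its power for a 1-minute shift, with no failures, is about 78% against 80% for the t-test if times are normal, and about 89% against 80% if lognormal.

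**The case for a change.** The strongest case for a change is that the omission is plain on the page, the remedy costs some wording and a few form fields, and completion status not recorded at the procedure may not be recoverable later. In the most adverse patterns the cuff-favouring error rises from 2.5% to between 11% and 19%. The reverse imbalance would mask the very benefit the trial is looking for.

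The omission stands, and so do the figures under their assumptions. Three things limit their weight.

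- The large figures need the very slowest patients to be lost, with none lost from the other arm. Nothing in the documents points to such a pattern. The protocol's expectation that the cuff eases insertion concerns speed and tip stability; it gives no completion rate.
- The items listed do imply an end point. Insertion, total withdrawal and total procedural time are recorded separately, so insertion naturally ends where withdrawal begins. That does not settle an incomplete case, but completed insertions are not left undefined in practice. As the list is open, the case report form may already hold completion status.
- Ranking failures worst, or censoring them in a log-rank test, changes the question. It compares a composite of speed and completion, whereas the objective is insertion time. One may argue that failure is itself a bad outcome, but then unequal failure moves the result by design.

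**Conclusion.** No change to the plan follows. This is missing detail that analysts fill sensibly: analyse by assigned arm, take insertion as ending when withdrawal starts, and report how many insertions were incomplete in each arm and how they were entered. No rule the plan states gives a wrong answer.

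Under a moderate link between failure and difficulty (assumed correlation 0.5), the shift runs from 0.03 minutes (3 vs 2 lost per 100) to 0.15 minutes (5 vs 0). That is 3% to 15% of the 1-minute target, with cuff-favouring error of 3.2% to 6.1% against 2.5%. If the slowest patients are the ones lost, the same imbalances give 0.07 to 0.35 minutes and 5.3% to 19.3%. With equal failure of the same kind in both arms there is no shift.

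All of this rests on assumed failure counts, an assumed mean of 6 minutes and a lognormal shape; the documents supply only the SD, the sample size and the target. A known, clearly unequal failure rate would alter this conclusion. The consequence for the trial's main claim is further limited because the Primary End-point section and the power statement both rest on inspection time. That they differ from the longer list of primary endpoints is a separate matter.
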